### **12.3. Appendix 3: Modified List of Highly Effective Methods for Avoiding Pregnancy in Females of reproductive potential**

This list does not apply to FRP with same sex partners, when this is their preferred and usual lifestyle or for subjects who are and will continue to be abstinent from penile-vaginal intercourse on a long term and persistent basis.

1. Contraceptive subdermal implant that meets the Prescribing Information effectiveness criteria including a <1% rate of failure per year, as stated in the Prescribing Information
2. Intrauterine device or intrauterine system that meets the Prescribing Information effectiveness criteria including a <1% rate of failure per year, as stated in the Prescribing Information [Hatcher, 2011]
3. Combined estrogen and progestogen oral contraceptive [Hatcher, 2011]
4. Injectable progestogen [Hatcher, 2011]
5. Contraceptive vaginal ring [Hatcher, 2011]
6. Percutaneous contraceptive patches [Hatcher, 2011]
7. Male partner sterilization with documentation of azoospermia prior to the female subject's entry into the study, and this male is the sole partner for that subject [Hatcher, 2011].

These allowed methods of contraception are only effective when used consistently, correctly and in accordance with the Prescribing Information. The investigator is responsible for ensuring that subjects understand how to properly use these methods of contraception.

**12.4. Appendix 4: Collection of Pregnancy Information**

- Investigator will collect pregnancy information on any female subject, who becomes pregnant while participating in this study
- Information will be recorded on the appropriate form and submitted to GSK within 2 weeks of learning of a subject's pregnancy.
- Subject will be followed to determine the outcome of the pregnancy. The investigator will collect follow up information on mother and infant, which will be forwarded to GSK. Generally, follow-up will not be required for longer than 6 to 8 weeks beyond the estimated delivery date.
- Any termination of pregnancy will be reported, regardless of fetal status (presence or absence of anomalies) or indication for procedure.
- While pregnancy itself is not considered to be an AE or SAE, any pregnancy complication or elective termination of a pregnancy will be reported as an AE or SAE.
- A spontaneous abortion is always considered to be an SAE and will be reported as such.
- Any SAE occurring as a result of a post-study pregnancy which is considered reasonably related to the study treatment by the investigator, will be reported to GSK as described in Section [12.6](#). Appendix 6. While the investigator is not obligated to actively seek this information in former study participants, he or she may learn of an SAE through spontaneous reporting.

**Any female subject who becomes pregnant while participating**

- will discontinue study medication or be withdrawn from the study

## 12.5. Appendix 5: Liver Safety Required Actions and Follow up Assessments

**Phase III-IV liver chemistry stopping and increased monitoring criteria** have been designed to assure subject safety and evaluate liver event etiology (in alignment with the FDA premarketing clinical liver safety guidance).

### Phase III-IV liver chemistry stopping criteria and required follow up assessments

Liver Chemistry Stopping Criteria - Liver Stopping Event	
ALT-absolute	ALT $\geq$ 8xULN
ALT Increase	ALT $\geq$ 5xULN but $<$ 8xULN persists for $\geq$ 2 weeks ALT $\geq$ 3xULN but $<$ 5xULN persists for $\geq$ 4 weeks
Bilirubin	ALT $\geq$ 3xULN and bilirubin $\geq$ 2xULN ( $>$ 35% direct bilirubin)
INR^2	ALT $\geq$ 3xULN and INR $>$ 1.5, if INR measured
Cannot Monitor	ALT $\geq$ 5xULN but $<$ 8xULN and cannot be monitored weekly for $\geq$ 2 weeks ALT $\geq$ 3xULN but $<$ 5xULN and cannot be monitored weekly for $\geq$ 4 weeks
Symptomatic	ALT $\geq$ 3xULN associated with symptoms (new or worsening) believed to be related to liver injury or hypersensitivity
Required Actions and Follow up Assessments following ANY Liver Stopping Event	
Actions	

 
Immediately discontinue study treatment
 
Report the event to GSK within 24 hours
 
Complete the liver event CRF and complete an SAE data collection tool if the event also meets the criteria for an SAE
 
Perform liver event follow up assessments
 
Monitor the subject until liver chemistries resolve, stabilize, or return to within baseline (see MONITORING below)
 
Do not restart/rechallenge subject with study treatment unless allowed per protocol and GSK Medical Governance approval is granted
 
If restart/rechallenge not allowed or not granted, permanently discontinue study treatment and may continue subject in the study for any protocol specified follow up assessments
 
 
MONITORING:
 
For bilirubin or INR criteria:
 
 
Repeat liver chemistries (include ALT, AST, alkaline phosphatase, bilirubin) and perform liver event follow up assessments within 24
 
	
 
Viral hepatitis serology
 
Only in those with underlying chronic hepatitis B at study entry (identified by positive hepatitis B surface antigen) and quantitative hepatitis B DNA
 
Blood sample for pharmacokinetic (PK) analysis, obtained within 24 hours after last dose
 
Serum creatine phosphokinase (CPK) and lactate dehydrogenase (LDH).
 
Fractionate bilirubin, if total bilirubin <math>\geq</math>2xULN
 
Obtain complete blood count with differential to assess eosinophilia
 
Record the appearance or worsening of clinical symptoms of liver injury, or hypersensitivity, on the AE report form
 
Record use of concomitant medications on the concomitant medications report form including acetaminophen, herbal remedies, other over the counter medications.
 
Record alcohol use on the liver event alcohol intake case report form
 
 
For bilirubin or INR criteria:


hrs
 
 
Monitor subjects twice weekly until liver chemistries resolve, stabilize or return to within baseline
 
A specialist or hepatology consultation is recommended
 
 
For All other criteria:
 
 
Repeat liver chemistries (include ALT, AST, alkaline phosphatase, bilirubin) and perform liver event follow up assessments within 24-72 hrs
 
Monitor subjects weekly until liver chemistries resolve, stabilize or return to within baseline
 
	
 
Anti-nuclear antibody, anti-smooth muscle antibody, Type 1 anti-liver kidney microsomal antibodies, and quantitative total immunoglobulin G (IgG or gamma globulins).
 
Serum acetaminophen adduct HPLC assay (quantifies potential acetaminophen contribution to liver injury in subjects with definite or likely acetaminophen use in the preceding week [James, 2009]).
 
Liver imaging (ultrasound, magnetic resonance, or computerised tomography) and /or liver biopsy to evaluate liver disease; complete Liver Imaging and/or Liver Biopsy CRF forms.
 


 
1. Serum bilirubin fractionation should be performed if testing is available. If serum bilirubin fractionation is not immediately available, discontinue study treatment for that subject if ALT <math>\geq</math> 3xULN and bilirubin <math>\geq</math> 2xULN. Additionally, (for ND patients only) if serum bilirubin fractionation testing is unavailable, record presence of detectable urinary bilirubin on dipstick, indicating direct bilirubin elevations and suggesting liver injury.
 
2. All events of ALT <math>\geq</math> 3xULN and bilirubin <math>\geq</math> 2xULN (<math>>35\%</math> direct bilirubin) or ALT <math>\geq</math> 3xULN and INR <math>>1.5</math>, if INR measured which may indicate severe liver injury (possible 'Hy's Law'), must be reported as an SAE (excluding studies of hepatic impairment or cirrhosis); INR measurement is not required and the threshold value stated will not apply to subjects receiving anticoagulants
 
3. New or worsening symptoms believed to be related to liver injury (such as fatigue, nausea, vomiting, right upper quadrant pain or tenderness, or jaundice) or believed to be related to hypersensitivity (such as fever, rash or eosinophilia)
 
4. Includes: Hepatitis A IgM antibody; Hepatitis B surface antigen and Hepatitis B Core Antibody (IgM); Hepatitis C RNA; Cytomegalovirus IgM antibody; Epstein-Barr viral capsid antigen IgM antibody (or if unavailable, obtain heterophile antibody or monospot testing); Hepatitis E IgM antibody or Hepatitis E RNA
 
5. PK sample may not be required for subjects known to be receiving placebo or non-GSK comparator treatments. Record the date/time of the PK blood sample draw and the date/time of the last dose of study treatment prior to blood sample draw on the CRF. If the date or time of the last dose is unclear, provide the subject's best approximation. If the date/time of the last dose cannot be approximated OR a PK sample cannot be collected in the time period indicated above, do not obtain a PK sample. Instructions for sample handling and shipping are in the SRM.
 
	

### Phase III-IV liver chemistry increased monitoring criteria with continued therapy

Liver Chemistry Increased Monitoring Criteria – Liver Monitoring Event	
Criteria	Actions
ALT $\geq$ 5xULN and $<$ 8xULN and bilirubin $<$ 2xULN without symptoms believed to be related to liver injury or hypersensitivity, and who can be monitored weekly for 2 weeks. OR ALT $\geq$ 3xULN and $<$ 5xULN and bilirubin	
 
Notify the GSK medical monitor within 24 hours of learning of the abnormality to discuss subject safety.
 
Subject can continue study treatment
 
Subject must return weekly for repeat liver chemistries (ALT, AST, alkaline phosphatase,
 

<2xULN without symptoms believed to be related to liver injury or hypersensitivity, and who can be monitored weekly for 4 weeks.
	
bilirubin) until they resolve, stabilise or return to within baseline
 

• If at any time subject meets the liver chemistry stopping criteria, proceed as described above

• If ALT decreases from ALT <math>\geq</math>5xULN and <8xULN to <math>\geq</math>3xULN but <5xULN, continue to monitor liver chemistries weekly.

• If, after 4 weeks of monitoring, ALT <3xULN and bilirubin <2xULN, monitor subjects twice monthly until liver chemistries normalize or return to within baseline.

--	--

## 12.6. Appendix 6: Definition of and Procedures for Recording, Evaluating, Follow-up and Reporting of Adverse Events

### 12.6.1. Definition of Adverse Events

#### Adverse Event Definition:

- An AE is any untoward medical occurrence in a patient or clinical investigation subject, temporally associated with the use of a medicinal product, whether or not considered related to the medicinal product.
- NOTE: An AE can therefore be any unfavorable and unintended sign (including an abnormal laboratory finding), symptom, or disease (new or exacerbated) temporally associated with the use of a medicinal product.

#### Events meeting AE definition include:

- Any abnormal laboratory test results (hematology, clinical chemistry, or urinalysis) or other safety assessments (e.g., ECGs, radiological scans, vital signs measurements), including those that worsen from baseline, and felt to be clinically significant in the medical and scientific judgement of the investigator.
- Exacerbation of a chronic or intermittent pre-existing condition including either an increase in frequency and/or intensity of the condition.
- New conditions detected or diagnosed after study treatment administration even though it may have been present prior to the start of the study.
- Signs, symptoms, or the clinical sequelae of a suspected interaction.
- Signs, symptoms, or the clinical sequelae of a suspected overdose of either study treatment or a concomitant medication (overdose per se will not be reported as an AE/SAE unless this is an intentional overdose taken with possible suicidal/self-harming intent. This should be reported regardless of sequelae).
- "Lack of efficacy" or "failure of expected pharmacological action" per se will not be reported as an AE or SAE. However, the signs and symptoms and/or clinical sequelae resulting from lack of efficacy will be reported if they fulfil the definition of an AE or SAE.

#### Events NOT meeting definition of an AE include:

- Any clinically significant abnormal laboratory findings or other abnormal safety assessments which are associated with the underlying disease, unless judged by the investigator to be more severe than expected for the subject's condition.
- The disease/disorder being studied or expected progression, signs, or symptoms of the disease/disorder being studied, unless more severe than expected for the subject's condition.
- Medical or surgical procedure (e.g., endoscopy, appendectomy): the condition that leads to the procedure is an AE.
- Situations where an untoward medical occurrence did not occur (social and/or convenience admission to a hospital).
- Anticipated day-to-day fluctuations of pre-existing disease(s) or condition(s) present or detected at the start of the study that do not worsen.

### 12.6.2. Definition of Serious Adverse Events

If an event is not an AE per definition above, then it cannot be an SAE even if serious conditions are met (e.g., hospitalization for signs/symptoms of the disease under study, death due to progression of disease, etc).

Serious Adverse Event (SAE) is defined as any untoward medical occurrence that, at any dose:	
a. Results in death	
b. Is life-threatening	
NOTE:	
The term 'life-threatening' in the definition of 'serious' refers to an event in which the subject was at risk of death at the time of the event. It does not refer to an event, which hypothetically might have caused death, if it were more severe.	
c. Requires hospitalization or prolongation of existing hospitalization	
NOTE:	

 
• In general, hospitalization signifies that the subject has been detained (usually involving at least an overnight stay) at the hospital or emergency ward for observation and/or treatment that would not have been appropriate in the physician's office or out-patient setting. Complications that occur during hospitalization are AEs. If a complication prolongs hospitalization or fulfills any other serious criteria, the event is serious. When in doubt as to whether "hospitalization" occurred or was necessary, the AE should be considered serious.
 
• Hospitalization for elective treatment of a pre-existing condition that did not worsen from baseline is not considered an AE.
 
	
d. Results in disability/incapacity	
NOTE:	

 
• The term disability means a substantial disruption of a person's ability to conduct normal life functions.
 
• This definition is not intended to include experiences of relatively minor medical significance such as uncomplicated headache, nausea, vomiting, diarrhea, influenza, and accidental trauma (e.g. sprained ankle) which may interfere or prevent everyday life functions but do not constitute a substantial disruption
 
	
e. Is a congenital anomaly/birth defect	
f. Other situations:	

 
• Medical or scientific judgment should be exercised in deciding whether reporting is appropriate in other situations, such as important medical events that may not be immediately life-threatening or result in death or hospitalization but may jeopardize the subject or may require medical or surgical intervention to prevent one of the other outcomes listed in the above definition. These should also be considered serious.
 
• Examples of such events are invasive or malignant cancers, intensive treatment in an emergency room or at home for allergic bronchospasm, blood dyscrasias or convulsions that do not result in hospitalization, or development of drug dependency or drug abuse
 
	
g. Is associated with liver injury and impaired liver function defined as:	

 
• ALT <math>\geq</math> 3xULN and total bilirubin* <math>\geq</math> 2xULN (>35% direct), or
 
• ALT <math>\geq</math> 3xULN and INR** <math>></math> 1.5.
 
	
* Serum bilirubin fractionation should be performed if testing is available; (for ND patients only) if	

unavailable, record presence of detectable urinary bilirubin on dipstick, indicating direct bilirubin elevations and suggesting liver injury. If fractionation is unavailable and ALT  $\geq$  3xULN and total bilirubin  $\geq$  2xULN, then the event is still to be reported as an SAE.

\*\* INR testing not required per protocol and the threshold value does not apply to subjects receiving anticoagulants. If INR measurement is obtained, the value is to be recorded on the SAE form.

### 12.6.3. Definition of Cardiovascular Events

#### Cardiovascular Events (CV) Definition:

Investigators will be required to fill out the specific CV event page of the CRF for the following AEs and SAEs:

- Myocardial infarction/unstable angina
- Congestive heart failure
- Arrhythmias
- Valvulopathy
- Pulmonary hypertension
- Cerebrovascular events/stroke and transient ischemic attack
- Peripheral arterial thromboembolism
- Deep venous thrombosis/pulmonary embolism
- Revascularization

### 12.6.4. Recording of AEs and SAEs

#### AEs and SAE Recording:

- When an AE/SAE occurs, it is the responsibility of the investigator to review all documentation (e.g., hospital progress notes, laboratory, and diagnostics reports) relative to the event.
- The investigator will then record all relevant information regarding an AE/SAE in the CRF
- It is not acceptable for the investigator to send photocopies of the subject's medical records to GSK in lieu of completion of the GSK, AE/SAE CRF page.
- There may be instances when copies of medical records for certain cases are requested by GSK. In this instance, all subject identifiers, with the exception of the subject number, will be blinded on the copies of the medical records prior to submission of to GSK.
- The investigator will attempt to establish a diagnosis of the event based on signs, symptoms, and/or other clinical information. In such cases, the diagnosis will be documented as the AE/SAE and not the individual signs/symptoms.
- PRO questionnaires and the collection of AE data are independent components of the study.
- Responses to each question in PRO questionnaire will be treated in accordance with standard scoring and statistical procedures detailed by the scale's developer.
- The use of a single question from a multidimensional health survey to designate a cause-effect relationship to an AE is inappropriate.

### 12.6.5. Evaluating AEs and SAEs

#### Assessment of Intensity

The investigator will make an assessment of intensity for each AE and SAE reported during the study and will assign it to one of the following categories:

- Mild: An event that is easily tolerated by the subject, causing minimal discomfort and not interfering with everyday activities.
- Moderate: An event that is sufficiently discomforting to interfere with normal everyday activities
- Severe: An event that prevents normal everyday activities. - an AE that is assessed as severe will not be confused with an SAE. Severity is a category utilized for rating the intensity of an event; and both AEs and SAEs can be assessed as severe.
- An event is defined as 'serious' when it meets at least one of the pre-defined outcomes as described in the definition of an SAE.

#### Assessment of Causality

- The investigator is obligated to assess the relationship between study treatment and the occurrence of each AE/SAE.
- A "reasonable possibility" is meant to convey that there are facts/evidence or arguments to suggest a causal relationship, rather than a relationship cannot be ruled out.
- The investigator will use clinical judgment to determine the relationship.
- Alternative causes, such as natural history of the underlying diseases, concomitant therapy, other risk factors, and the temporal relationship of the event to the study treatment will be considered and investigated.
- The investigator will also consult the Investigator Brochure (IB) and/or Product Information, for marketed products, in the determination of his/her assessment.
- For each AE/SAE the investigator must document in the medical notes that he/she has reviewed the AE/SAE and has provided an assessment of causality.
- There may be situations when an SAE has occurred and the investigator has minimal information to include in the initial report to GSK. However, **it is very important that the investigator always make an assessment of causality for every event prior to the initial transmission of the SAE data to GSK.**
- The investigator may change his/her opinion of causality in light of follow-up information, amending the SAE data collection tool accordingly.
- The causality assessment is one of the criteria used when determining regulatory reporting requirements.

#### Follow-up of AEs and SAEs

- The investigator is obligated to perform or arrange for the conduct of supplemental measurements and/or evaluations as may be indicated or as requested by GSK to elucidate as fully as possible the nature and/or causality of the AE or SAE.
- The investigator is obligated to assist. This may include additional laboratory tests or investigations, histopathological examinations or consultation with other health care professionals.
- If a subject dies during participation in the study or during a recognized follow-up period, the investigator will provide GSK with a copy of any post-mortem findings, including

histopathology.

- New or updated information will be recorded in the originally completed CRF.
- The investigator will submit any updated SAE data to GSK within the designated reporting time frames.

#### 12.6.6. Reporting of SAEs to GSK

##### SAE reporting to GSK via electronic data collection tool

- Primary mechanism for reporting SAEs to GSK will be the electronic data collection tool
- If the electronic system is unavailable for greater than 24 hours, the site will use the paper SAE data collection tool and fax it to the SAE contact.
- Site will enter the serious adverse event data into the electronic system as soon as it becomes available.
- After the study is completed at a given site, the electronic data collection tool (e.g., InForm system) will be taken off-line to prevent the entry of new data or changes to existing data
- If a site receives a report of a new SAE from a study subject or receives updated data on a previously reported SAE after the electronic data collection tool has been taken off-line, the site can report this information on a paper SAE form or to the SAE contact by telephone.
- Contacts for SAE receipt can be found at the beginning of this protocol on the Sponsor/Medical Monitor Contact Information page.

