**7.4.1.1. Time period and Frequency for collecting AE and SAE information**

- AEs and SAEs will be collected from the start of Study Treatment until the follow-up contact (see Section 7.4.1.3.), at the timepoints specified in the Time and Events Table (Table 13).
- Medical occurrences that begin prior to the start of study treatment but after obtaining informed consent may be recorded on the Medical History/Current Medical Conditions section of the CRF.
- Any SAEs assessed as related to study participation (e.g., protocol-mandated procedures, invasive tests, or change in existing therapy) or related to a GSK product will be recorded from the time a subject consents to participate in the study up to and including any follow-up contact.
- All SAEs will be recorded and reported to GSK within 24 hours, as indicated in Section 12.6. Appendix 6.
- Investigators are not obligated to actively seek AEs or SAEs in former study subjects. However, if the investigator learns of any SAE, including a death, at any time after a subject has been discharged from the study, and he/she considers the event reasonably related to the study treatment or study participation, the investigator must promptly notify GSK.

NOTE: The method of recording, evaluating and assessing causality of AEs and SAEs plus procedures for completing and transmitting SAE reports to GSK are provided in Section 12.6. Appendix 6.

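### The paper fallback for SAE reports opens only after more than 24 hours of system outage, no sooner than the 24-hour reporting deadline it should protect, so some SAEs can be late while the rule is followed

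*Protocol*

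**What the plan says.** Protocol Section 7.4.1.1 sets the deadline and says where the procedure is found: "All SAEs will be recorded and reported to GSK within 24 hours, as indicated in Section 12.6. Appendix 6".

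Appendix 6, Section 12.6.6 gives the procedure:

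- Main route: "Primary mechanism for reporting SAEs to GSK will be the electronic data collection tool".
- Outage rule, under which the paper form goes by fax: "If the electronic system is unavailable for greater than 24 hours, the site will use the paper SAE data collection tool".
- Data entry: "Site will enter the serious adverse event data into the electronic system as soon as it becomes available".
- Paper or telephone, once the tool is closed at the end of a site's participation: "after the electronic data collection tool has been taken off-line, the site can report this information on a paper SAE form or to the SAE".

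The last item is the only paper or telephone route in Section 12.6.6 that carries no waiting period, and it applies only after closure at the site. Appendix 6 does not repeat the 24-hour limit; under follow-up of AEs and SAEs it refers only to designated time frames. Neither section says when its 24 hours begin.

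The protocol file holds more than one copy of Section 12.6.6, and the outage sentence is the same in each. The two copies that come with a visible Section 7.4.1.1 (Amendment 01 and the other full protocol text) both show the mismatch. A further copy, which adds a 72-hour step for confirming causality, comes without its Section 7.4.1.1, so the conflict cannot be checked in that version.

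**The concern.** A backup route exists so that the deadline can be met when the main route fails. Here the backup waits for longer than the deadline allows. A site that follows Section 12.6.6 to the letter can find that its only stated options are to wait for the system or to wait for the paper route to open, while the limit in Section 7.4.1.1 runs out. Following the cross-reference does not help, because Appendix 6 gives the outage rule but not the deadline.

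What is at stake is timely receipt of SAEs by the sponsor. The study is open-label, and Appendix 2 relies on in-stream monitoring of events of special interest by an internal safety review team. That monitoring depends on reports arriving when the protocol says they will. A site could also be recorded as non-compliant with one section for having complied with another.

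**Working it through.** The plan gives no derived figure to reproduce; its two inputs are both durations.

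- Deadline: 24 h (Section 7.4.1.1).
- Fallback trigger: system unavailable for more than 24 h (Section 12.6.6).

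Set the start of the outage at hour 0 and let it last D hours. The site becomes aware of the SAE at hour t, where a negative t means aware before the outage with the report still unsent. Assume that the reporting clock starts at awareness. Then:

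- Deadline = t + 24.
- Reading A, trigger counted from the start of the outage: first stated route = hour D if D ≤ 24. If D > 24, it is paper just after hour 24, or at once for an SAE learned later than that.
- Reading B, trigger counted from the site's first failed attempt, taken to be at max(t, 0): first stated route = the earlier of hour D and just after max(t, 0) + 24.
- Margin = deadline − first stated route.

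| t (h) | D (h) | Deadline (hour) | First route, A | Margin, A | First route, B | Margin, B |
|---|---|---|---|---|---|---|
| −20 | 6 | 4 | system, 6 | 2 h late | system, 6 | 2 h late |
| −12 | 6 | 12 | system, 6 | 6 h spare | system, 6 | 6 h spare |
| −12 | 24 | 12 | system, 24 | 12 h late | system, 24 | 12 h late |
| −6 | 36 | 18 | paper, just after 24 | 6 h late | paper, just after 24 | 6 h late |
| 0 | 36 | 24 | paper, just after 24 | just late | paper, just after 24 | just late |
| 1 | 36 | 25 | paper, just after 24 | about 1 h spare | paper, just after 25 | just late |
| 12 | 48 | 36 | paper, just after 24 | about 12 h spare | paper, just after 36 | just late |
| 23 | 36 | 47 | paper, just after 24 | about 23 h spare | system, 36 | 11 h spare |

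Three results follow.

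1. SAE known a hours before the outage and unsent (t = −a). Only 24 − a hours remain when the system fails. Under either reading the report is late whenever D > 24 − a, by min(D, 24) − (24 − a) hours. For a = 6 and D = 36: 24 − 18 = 6 h. For a = 12 and D = 24: 24 − 12 = 12 h, and paper never opens because the outage does not exceed 24 h.
2. SAE learned after the outage began, reading A. Paper opens just after hour 24 and the deadline is hour 24 + t, so about t hours remain. The report can be on time, with little room when t is small. If D ≤ 24, the system is back before the deadline.
3. SAE learned after the outage began, reading B. Paper opens just as the deadline passes. The report is late whenever the outage runs more than 24 h beyond awareness, and on time otherwise.

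**The case against.** The strongest reply is that the natural reading of the outage rule counts from when the system went down. An SAE learned during the outage can then be sent on time, and an outage of 24 hours or less needs no second route for such an SAE. The electronic tool is also called the primary mechanism, not the only one; nothing in Section 12.6.6 forbids an earlier call to the SAE contact, and the duty in Section 7.4.1.1 stays in force throughout. The study reference manual and the contact page were not available for this check and may give further instructions.

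Much of this stands, and it rules out three stronger readings that a reader might infer.

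- That any SAE caught in an outage is late, or that a site following Section 12.6.6 necessarily breaches Section 7.4.1.1. Under reading A, forced lateness is confined to SAEs known but unsent when the system fails, plus the boundary case of awareness at the moment of failure with an outage over 24 h.
- That the rule causes a delay of about 48 hours. That total needs a site to have held the SAE for almost 24 hours with a working system, followed by 24 hours of waiting for paper. Up to half of it is the site's own delay.
- That liver stopping events are held back in the same way. Appendix 5 lists the 24-hour report to the sponsor separately from completing the SAE tool, and has the medical monitor notified within 24 hours of liver monitoring events. Neither notice is tied to the electronic system or its outage rule.

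The reply does not remove the gap. The only alternative stated for an outage during the study carries the wait of more than 24 hours, and a site should not have to infer that it may use another.

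**Conclusion.** The point holds in a limited form. The fallback trigger is no shorter than the reporting deadline, and no other route is stated for an outage during the study. An SAE already known but unsent when the system fails can miss the deadline while the rule is followed, by 2 to 12 hours in the late cases worked above with prior awareness. If the trigger is counted from the site's failed attempt, so can one learned during an outage that lasts more than 24 hours beyond awareness, though then the stated route opens just as the limit passes. If the trigger is counted from outage start, an SAE learned after the outage begins can still be on time.

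This assumes that the deadline runs from site awareness and that the site uses only the routes Section 12.6.6 states. The protocol gives no outage frequency, so the number of affected reports cannot be estimated and may be small. The point concerns safety reporting alone; the primary analysis, power and type I error are untouched. It should be corrected because two sections on the same duty conflict and the remedy is simple.

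**What to change.** Reconcile Section 7.4.1.1 with Section 12.6.6, in every version of the appendix still in use.

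- Tie the fallback to the deadline and not to the length of the outage: if the electronic system is not available in time to meet the 24-hour limit, the site sends the existing paper SAE form to the SAE contact within that limit, and enters the data electronically once the system is back.
- State when the 24-hour reporting clock starts.
- State the 24-hour limit in Appendix 6, to which Section 7.4.1.1 refers.

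The cost is a sentence or two in the protocol and matching text in the study reference manual. The paper form, fax route and SAE contact already exist. Section 7.4.4.3 already handles medical device incidents this way: a 24-hour limit, fax preferred, telephone acceptable without a fax machine, and the same contact as for SAEs.
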